3.9 Discontinuation of investigational product

Patients may be discontinued from IP in the following situations:

- Patient decision. The patient is at any time free to discontinue treatment, without prejudice to further treatment
- An adverse event that, in the opinion of the Investigator or AstraZeneca, warrants discontinuation from further dosing
- Patient noncompliance that, in the opinion of the Investigator or sponsor, warrants withdrawal (e.g. refusal to adhere to scheduled visits)
- Patient is determined to have met one or more of the exclusion criteria or failed to meet all of the inclusion criteria for study participation at study entry and continuing IP, in the decision of the Investigator, might constitute a safety risk

If the patient is discontinued from IP, the scheduled study visits, data collection and procedures should continue according to the Clinical Study Protocol (CSP) until study closure. Alternatively, if the subject does not agree to this option, a modified follow up through e.g., regular telephone contacts or a contact at study closure should be arranged, if agreed to by the subject and in compliance with local data privacy laws/practices. The approach taken should be registered in the CRF.

If patient is required to or chooses to discontinue the IP, every reasonable effort should be made for the patient to remain in the study for follow-up and to complete all other study procedures until the scheduled end of the study.

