6.2.3 Phase

For the purpose of safety analyses, analysis phase will be defined in terms of study days since the first day of the study medication, as illustrated in the following table:

Phase	Phase Window for Analysis (Days)
Baseline phase	before first dose of study IP (day <1 ^a)
On-treatment phase	From day 1^{b} to ≤ 7 days after last dose of study drug
Off-treatment phase	>7 days after last dose of study drug

Table 4: Analysis phases

a Includes all measurements collected before first dose of IP. If the measurement is collected on the day of first dose of IP but the time of collection (or the planned timepoint) cannot determine if the measurement was before or after first dose of IP, then it will be considered as collected after first dose of IP except for ECGs, Vital Signs and Physical examinations which are considered as pre-dose measurements as per protocol.

^b Includes all measurements collected on the day of first dose of IP (Day 1), at the time of IP intake and after.

6.3 **Baseline Assessments**

The baseline value used for statistical analyses is the last available value among those in the Baseline visit windows, prior to first dose of IP, except for PRO questionnaires. As reported in the footnote (a) of table 4, if the measurement is collected on day 1 but it cannot be determined if the measurement was done before or after the first dose of IP (due to missing time or planned time point flag or missing time of first dose of IP), then it will be considered as collected after the first dose of IP. There is one exception to that for ECGs, Vital Signs and Physical examinations which are considered as pre-dose measurements as per protocol. If several measurements are collected on the last date (same day) prior to the first day of IP, or on the first day of IP prior to the first dose, the baseline value will be the average (for numeric values)/worst (for categorical values) of the measurements.

	Distribution:	Original:	Copy:
TPCA025 Vers (based on TPQA	2 3		Effective Date: 27 th August 2017 Prior Effective Date: 21 st December 2016

CONFIDENTIAL AND PROPRIETARY

Sponsor:	AstraZeneca AB	Protocol/CIP Number:	D7550C00003
CIL Project Number:	40343		

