After the imputation of the AE becomes serious as described in section 7.3, the SAE will be assigned to the period where it starts according to the following algorithm:

- If the date in which the AE becomes serious is prior to the date of the first dose of IP, then the SAE will be assigned to the Baseline phase,
- If the date in which the AE becomes serious is on or after the date of the first dose of IP through 7 days after the date of last dose of IP (inclusive), then the SAE will be assigned to the On-treatment phase,
- If the date in which the AE becomes serious is after the date of last dose of IP + 7 days, then the SAE will be assigned to the Off-treatment phase.

If the date in which the AE became serious is completely missing, the SAE will be assigned according to the AE start date and time.

The SAE assignation is used only to identify cases in which the AE starts as Non-serious in the On-treatment phase and becomes Serious in the Off-treatment phase. In cases like these, the AE will be reported as one single AE in the listings, but it will be summarized as one non-serious AE in the On-treatment tables and one SAE in the Off-treatment tables.

TPCA025 Version 2 (based on TPQA036 Version 2) Original:

Copy:

Effective Date: 27th August 2017 Prior Effective Date: 21st December 2016

Distribution:

Sponsor:	AstraZeneca AB	Protocol/CIP Number:	D7550C00003
CIL Project Number:	40343		

Second IA and final analysis considerations

If the AE started in the on-treatment phase and became serious in the off-treatment phase, the AE will be considered as serious from the start, i.e. in the on-treatment phase as well. The AE will be reported as one single record in the listing.

A drug-related AE is defined as any AE with a reasonable possibility of causal relationship to study treatment as assessed by the investigator or with missing assessment of the causal relationship.

The coding dictionary for this study will be the Medical Dictionary for Regulatory Activities (MedDRA) version 20.0 or higher.

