8.8.2 Adverse Events

AEs will be assigned to the study phases as described in section 6.6.2.

Unless otherwise specified, AEs and SAEs will be summarized using the Safety Analysis Set by treatment group and by cohort of patients. Percentages will be based on the total numbers of subjects in the treatment group.

Subjects with multiple events in the same category will be counted only once in that category. Subjects with events in more than 1 category will be counted once in each of those categories. Unless otherwise specified On-treatment and Off-treatment phases will be reported separately for each summary table.

The following summary tables will be reported:

An overview table for all the AEs.

The number and percentage of subjects with the most common AEs (frequency>3%) for each Preferred Term (PT);

Distribution:

Original:

Copy:

TPCA025 Version 2 (based on TPQA036 Version 2) Effective Date: 27th August 2017 Prior Effective Date: 21st December 2016

Sponsor:	AstraZeneca AB	Protocol/CIP Number:	D7550C00003
CIL Project Number:	40343		

The number and percentage of subjects with any AEs for each System Organ Class (SOC) and PT;

The number and percentage of subjects with any AEs by maximum intensity for each PT;

The number and percentage of subjects with any AEs by investigator's causality assessment for each PT;

The number and percentage of subjects with AEs with outcome of death for each SOC and PT;

The number and percentage of subjects with AEs with outcome of death and with causality related to study drug for each SOC and PT in the On-treatment phase.

Key subject information for all subjects with AEs with outcome of death (On-treatment and Off-treatment phases together in the same table).

Time from first dose to AE (day) will be calculated as start date of the AE minus date of first dose +1. Time from last dose to death (day) will be calculated as death date minus date of last dose +1. Time from first dose to death (day) will be calculated as death date minus date of first dose +1. Durations will be calculated only for fully completed dates.

The number and percentage of subjects with death.

The number and percentage of subjects with any SAEs for each SOC and PT;

The number and percentage of subjects with any SAEs with causality related to study drug for each SOC and PT in the On-treatment phase.

Key subject information for all subjects with SAEs.

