Table 14.3.2.15 - Adverse events with outcome of death, causally related to study treatment - Cohort 4 weeks treatment and Cohort 12 weeks treatment - On treatment (Safety Analysis Set) Table 14.3.2.16 - Adverse events with outcome of death - Cohort 4 weeks treatment and Cohort 12 weeks treatment - key subject information (Safety Analysis

Set)

Table FDAAA1-1 - Non-serious adverse events occurring in greater than 5% of subjects - Cohort 4 weeks treatment and Cohort 12 weeks treatment - On Trable FDAAA1-2 - Non-serious adverse events occurring in greater than 5% of subjects - Cohort 4 weeks treatment and Cohort 12 weeks treatment - Off

treatment (Safety Analysis Set)

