14.3.4 Serious adverse events

Table 14.3.4.1 - Serious adverse events, by system organ class and preferred term - Cohort 4 weeks treatment and Cohort 12 weeks treatment - On treatment (Safety Analysis Set)

Table 14.3.4.2 - Serious adverse events, by system organ class and preferred term - Cohort 4 weeks treatment and Cohort 12 weeks treatment - Off treatment (Safety Analysis Set) Table 14.3.4.3 - Serious adverse events, causally related to study treatment - Cohort 4 weeks treatment and Cohort 12 weeks treatment - On treatment (Safety

Table 14.3.4.4 - Serious adverse events - Cohort 4 weeks treatment and Cohort 12 weeks treatment - key subject information (Safety Analysis Set)

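### The related-SAE and related-death tables cover only the On-treatment phase, so a related event starting more than 7 days after last dose enters no table specified as a count of them

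*SAP*

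**What the plan says.** SAP 8.8.2 sets a default for adverse event summaries: "Unless otherwise specified On-treatment and Off-treatment phases will be reported separately for each summary table". It then departs from that default for two summaries that combine causality with a serious outcome. One is "The number and percentage of subjects with any SAEs with causality related to study drug for each SOC and PT in the On-treatment phase". The other concerns "AEs with outcome of death and with causality related to study drug for each SOC and PT in the On-treatment phase".

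The Section 12 table list matches the text. Table 14.3.4.3 is titled "Serious adverse events, causally related to study treatment - Cohort 4 weeks treatment and Cohort 12 weeks treatment - On treatment" and Table 14.3.2.15 is titled "Adverse events with outcome of death, causally related to study treatment - Cohort 4 weeks treatment and Cohort 12 weeks treatment - On treatment". Neither has an Off-treatment version.

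SAP 6.2.3 (Table 4) defines the Off-treatment phase as ">7 days after last dose of study drug", and SAP 6.6.2 assigns an AE to a phase by its start date. SAP 6.6.2 also defines a drug-related AE as one with a reasonable possibility of a causal relationship "as assessed by the investigator or with missing assessment of the causal relationship". That definition has no phase limit. Protocol 6.3.1 collects AEs from first dose through follow-up, and Protocol 1.4 places Visit 5 at 4 weeks (± 4 days) after last dose.

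**The concern.** AEs are collected, and causality is judged, for about 28 days after the last dose. The two counts a safety reader is likely to look for first, drug-related SAEs and drug-related deaths, stop 7 days after it. The SAP gives no reason for leaving its both-phases default here, and Protocol 8.5.3 defines the phases without confining causality summaries to one of them.

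If a related SAE starts after day 7, the report will contain a related-SAE table without it. A reader who takes that table as the study total would undercount. In a trial of about 138 randomized patients few such events are likely, so a single omission would visibly change the figure.

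**Working it through.** The plan states no figure to reproduce. The check compares the SAP text with the table list and then sizes the uncovered window.

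**1. Tables by phase (SAP Section 12)**

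| Summary | On-treatment | Off-treatment |
|---|---|---|
| AEs by causality and PT | 14.3.2.9, 14.3.2.10 | 14.3.2.11, 14.3.2.12 |
| All fatal AEs | 14.3.2.13 | 14.3.2.14 |
| Related fatal AEs | 14.3.2.15 | none |
| All deaths | 14.3.3.1 | 14.3.3.2 |
| All SAEs | 14.3.4.1 | 14.3.4.2 |
| Related SAEs | 14.3.4.3 | none |
| AEs leading to IP discontinuation | 14.3.5.1 | none |
| Related AEs leading to IP discontinuation | 14.3.5.2 | none |
| AEs leading to IP interruption | 14.3.5.4 | none |

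The discontinuation and interruption tables are On-treatment by nature, because those actions need ongoing dosing. That reason does not apply to SAEs or deaths.

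**2. Where a related SAE starting on day 8 or later after last dose would appear**

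- Table 14.3.4.2: yes, but without causality.
- Table 14.3.2.11 or 14.3.2.12: yes, but mixed with non-serious events.
- Key-subject Table 14.3.4.4, whose title carries no phase limit, and AE listing 16.2.7.1: yes, as individual records and not as a count.
- If fatal, also Table 14.3.2.14 and key-subject Table 14.3.2.16, which SAP 8.8.2 says combines both phases.
- Off-treatment overview Table 14.3.2.2: unknown, because its rows are not specified.

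No table specified as a related-SAE or related-death count includes it.

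**3. Size of the window**

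Inputs: Visit 5 at 28 days (± 4) after last dose (Protocol 1.4 and Table 1); On-treatment phase to 7 days after last dose (SAP 6.2.3); nominal Visit 5 on day 56 or day 112 (SAP Table 3).

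Uncovered days = days from last dose to Visit 5, minus 7.

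- Nominal: 28 − 7 = 21 days.
- Range: 24 − 7 = 17 to 32 − 7 = 25 days.
- Share of post-dose follow-up: 21/28 = 75%.
- Share of the nominal collection period: 21/56 = 37.5% in the 4-week cohort and 21/112 = 18.75% in 12-week completers.

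These are shares of calendar time, not of events.

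**4. Which events are affected**

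Under the SAP 6.6.2 rule for the second interim and final analyses, an AE that starts On-treatment and becomes serious Off-treatment is treated as serious On-treatment. Because phase follows start date, an AE that starts within 7 days of last dose and later proves fatal also stays On-treatment. Only new-onset events after day 7 fall outside.

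**5. An example from the protocol**

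Appendix D defines Potential Hy's Law at any point after the start of study medication and requires such a case to be reported as an SAE with causality recorded as related. Protocol Table 1 schedules safety laboratory tests at Visit 5 and none between the end of treatment and Visit 5. A case first shown by those tests, with onset dated then, starts 24 to 32 days after last dose and is Off-treatment. It would be missing from Table 14.3.4.3. Tables 14.3.7.8 and 14.3.7.9 would not show it either, because they use maximum on-treatment values. Protocol 1.3 names transaminase elevation among the preclinical risks.

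**The case against.** The strongest reply is that nothing is lost. Every such event appears in several planned outputs, the causality judgement is tabulated Off-treatment in 14.3.2.11 and 14.3.2.12, and what is missing is one cross-tabulation, serious by related. Tables 14.3.4.3 and 14.3.2.15 are labelled On-treatment and are correct for that period, and the 7-day boundary is prespecified in Protocol 8.5.3. The three tables restricted to causally related events (14.3.2.15, 14.3.4.3 and 14.3.5.2) follow one convention. The rows of overview Table 14.3.2.2 are unspecified and might include related SAEs. All of this stands, and it limits the point to a missing count. It does not supply that count.

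Some stronger readings are tempting but not supported:

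- A reader might infer that the 7-day rule overrides the investigator's judgement or the missing-counts-as-related rule. It does neither, since the definition in SAP 6.6.2 applies in both phases.
- A reader might infer a bias between arms, because Protocol 3.9 says that after stopping IP "the scheduled study visits, data collection and procedures should continue according to the Clinical Study Protocol (CSP) until study closure", so an arm with more early stops would have more uncovered time. A 12-week patient who stopped at day 28 and was followed to day 112 would have 112 − 35 = 77 uncovered days of 112 (69%). But the documents give no stopping rate or event rate. Protocol 3.9 also allows a modified follow-up, and Table 1 dates Visit 5 from the last dose. An AE that causes stopping normally starts before or around the last dose and so counts On-treatment. More Off-treatment days do not by themselves mean more related SAEs left out.

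**Conclusion.** The point holds as a stated restriction that leaves a gap in two safety counts. New-onset related SAEs and related fatal AEs starting more than 7 days after last dose enter no table specified as a count of them, over a nominal window of 21 days (17 to 25). This assumes that Visit 5 takes place as scheduled and that overview Table 14.3.2.2 has no related-SAE row. The number of events affected cannot be estimated from the documents and is probably small. No estimate, test, power or type I error is affected, and no difference between arms is shown. It is a cheap improvement to reporting, worth making because the whole-period count would otherwise have to be rebuilt by hand from individual records.

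**What to change.** In SAP 8.8.2 and Section 12, add Off-treatment counterparts of Tables 14.3.4.3 and 14.3.2.15. Alternatively, replace each with one table covering the whole period after first dose, with the On-/Off-treatment split shown. Apply the existing rule that missing causality counts as related in both phases.

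The cost is a change of SAP wording and two more tables, or extra columns in two tables, from data already collected under Protocol 6.3. The downside for the sponsor is that the related-SAE count may look slightly less favourable.

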8.8.3 Clinical Laboratory Evaluations

Clinical laboratory evaluation is performed based on the Safety Analysis Set. The list and the assessment of all Clinical Laboratory variables are reported section 6.6.3.

Laboratory test results for haematology, coagulation and clinical chemistry

Laboratory test results for haematology, coagulation and clinical chemistry will be summarized in AZ preferred units for each treatment group, and for change from baseline at each visit. Change from baseline to each post-baseline visit will be calculated as the postbaseline visit value minus the baseline visit value.

Classification of the laboratory values with respect to the normal reference range will be provided (low/normal/high). Shifts from baseline to maximum/minimum value during Ontreatment phase of this classification will be presented for each treatment group and by cohort of patients.

Hy's law criteria will also be summarized in a double-entry table by cohort of patients.

Distribution:

Original:

Copy:

TPCA025 Version 2 (based on TPQA036 Version 2) Effective Date: 27th August 2017 Prior Effective Date: 21st December 2016

Sponsor:	AstraZeneca AB	Protocol/CIP Number:	D7550C00003
CIL Project Number:	40343		

Laboratory test results for urinalysis

Laboratory test results for quantitative variables (i.e. creatinine and albumin) will be summarized in AZ preferred units for each treatment group, and for change from baseline at each visit. Change from baseline to each post-baseline visit will be calculated as the post-baseline visit value minus the baseline visit value.

Shifts from baseline to maximum value during On-treatment phase will be presented for semi-quantitative variables (i.e. albumin, protein, blood, glucose and Leukocytes). All laboratory data for haematology, coagulation, clinical chemistry and urinalysis will be also presented in listings.

8.8.4 Other Observations Related to Safety

Vital Signs

Vital signs [pulse, pulse oximetry, systolic and diastolic blood pressure] will be summarized for each treatment group, and for change from baseline at each visit based on the Safety Analysis Set. Change from baseline to each post-baseline visit will be calculated as the post-baseline visit value minus the baseline visit value.

The list and the assessment of all Vital Signs variables are reported section 6.6.4.

Vital signs will be also presented in listings including flags for values outside of the reference ranges. Reference ranges are:

- Systolic Blood Pressure: 80-180 mmHg;
- Diastolic Blood Pressure: 50-120 mmHg;
- Pulse: 50-95 beats/min;
- Pulse oximetry: 90-100%.

Also, vital signs associated to CFVR are listed but not used for any statistical analysis.

Electrocardiogram

ECG summaries will be based on the Safety Analysis Set. ECGs details are provided in section 6.6.4. Shifts from baseline to last On-treatment observation will be presented for overall ECG result by cohort of patients. Abnormal 12-lead ECG findings will be presented in listings.

Physical Findings

The list and the assessment of all Physical findings are reported in section 6.6.4. Physical examination results will be collected as:

- normal,
- abnormal but non-clinically significant,
- abnormal clinically significant.

Summary will be based on the Safety Analysis Set.

Distribution:

Original:

Copy:

TPCA025 Version 2 (based on TPQA036 Version 2)

Sponsor:	AstraZeneca AB	Protocol/CIP Number:	D7550C00003
CIL Project Number:	40343		

Body Weight and BMI

Body weight and BMI details are provided in section 6.6.4. Body weight and BMI will be summarized using the Safety Analysis Set.

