1.3 Benefit/risk and ethical assessment

AZD5718 has been administered to 84 healthy subjects (in completed studies or studies in reporting phase) in single doses up to 1200mg, and in repeated doses up to 600 mg for 10 days. The compound has been well tolerated in healthy subjects. No clinically meaningful differences for changes over time in clinical laboratory tests, vital signs or electrocardiograms (ECGs) were observed between subjects who received AZD5718 and those who received placebo. There were no deaths or serious adverse events (SAEs) and all subjects completed the studies. The most common adverse event (AE) was headache. No safety concerns were raised during the studies.

Preclinical safety studies have identified several potential risks including transaminase elevations, pharyngeal and gastric mucosal lesions and delayed gastric emptying, plasma glucose elevation, minimal hypertrophy of thyroid follicular cells and potential effects on heart rate and blood pressure. None of these findings were observed in the clinical studies performed to date. The preclinical safety findings are described in more detail in the Investigators Brochure.

Based on knowledge of the mechanism of action, previous clinical experience and the preclinical safety studies the potential risks will be closely monitored. No specific harms are anticipated from participating to this trial. Available preclinical and clinical data suggest that the subjects may benefit from participation in the study as inhibition of 5-LO pathway may improve coronary microvascular function, reduce coronary artery plaque progression and

improve left ventricle ejection fraction. Based on prior SMAD study, the effect of AZD5718 can be detected in decreased u-LTE₄ concentrations under the designed 4 weeks of study treatment period, though potentially reaching even more stable and sustainable effect with the treatment prolongation up to 12 weeks.

The extended treatment period up to 12 weeks, will also provide with more complete safety profile data in CAD patients (post-ACS population) with longer treatment exposure.

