3.2 Exclusion criteria

Patients should not enter the study if any of the following exclusion criteria are fulfilled:

- 1 Alanine aminotransferase (ALT) >2 x ULN (i.e., above the normal range) at visit 2, cirrhosis, recent hepatitis, or positive screening test for hepatitis B (hepatitis B surface antigen) or hepatitis C
- 2 Uncontrolled Type 1 or Type 2 diabetes defined as haemoglobin A1c (HbA1c) Diabetes Control and Complications Trial (DCCT) > 9% or International Federation of Clinical Chemistry (IFCC) >74.9 mmol/mol
- 3 Patients with atrial fibrillation (chronic or current) or history of ventricular tachycardia requiring therapy for termination, or symptomatic sustained ventricular tachycardia or sick sinus syndrome or AV blockage degree 2-3
- 4 Patients with pacemaker
- 5 Prior coronary artery by-pass graft (CABG) to LAD
- 6 Left ventricle ejection fraction < 30%
- 7 Unacceptable level of angina despite maximal medical therapy or unstable angina at entry Canadian Cardiovascular Society (CCS) ≥ 3 (Visit 1 or Visit 2)
- 8 Stroke within the previous 6 months from ACS or ongoing treatment with Persantin or Asasantin
- 9 Planned treatment with zileuton, leukotriene receptor antagonists (e.g. montelukast), coumadin or steroids during trial
- 10 Planned statin therapy dose regimen changes during trial
- 11 Chronic use of anticoagulants on therapeutic dose (not including thrombosis prophylaxis) during the study
- 12 Planned additional cardiac intervention (e.g., PCI, CABG) within next 6 months
- 13 NYHA class III-IV heart failure or decompensated heart failure at discharge or hospitalization for exacerbation of chronic heart failure within the previous 3 months from ACS
- 14 Previously known severe renal disease (CKD stage 4 or 5) or previously known creatinine clearance calculated by Cockcroft Gault equation <30 ml/min*m²
- 15 Aortic or mitral valvular disease or valvular disease classified as severe
- 16 Known allergy to adenosine and mannitol, or experience of previous adverse effects of adenosine stress testing
- 17 Known elevated intracranial pressure
- 18 Heart rate < 40 bpm
- 19 Systolic blood pressure < 90 mmHg
- 20 Asthma or COPD with strong reactive component in judgment of investigator
- 21 Treatment with dipyridamole, theophyllamine, fluvoxamine, rifampicin, fenytoin or carbamazepine
- 22 Inability to comply with the study protocol

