5.2.5 Vital signs

Vital signs will include pulse, and systolic and diastolic blood pressure. Vital signs will be obtained at time points indicated in Section 4, Table 1 (and ad-hoc as medically indicated).

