For visit windows 3, 4, 4b, 4c and 5 if more than one measurement of the variable (scheduled or unscheduled visit) falls in the same visit window but in different days, the nearest to the scheduled visit day will be taken. If several measurements are collected within the same distance from the scheduled study day, the data of the latest visit after the scheduled study day within that window will be used.

If several measurements are collected during the selected day, the average (for numeric values)/worst (for categorical values) of the measurements will be taken. For numeric values, the analysed value will be the arithmetic mean for normal distributed variables and the geometric mean for log-normal distributed variables.

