14.3.8 Vital signs, ECG, physical findings and other observations

Table 14.3.8.1 - Vital signs variables, over time (Safety Analysis Set)

Table 14.3.8.2 - Physical examination variables, over time (Safety Analysis Set)

Table 14.3.8.3 - Body Weight and BMI, over time (Safety Analysis Set)

Table 14.3.8.4 - ECG baseline versus last observation on treatment - Cohort 4 weeks treatment (Safety Analysis Set)

Table 14.3.8.5 - ECG, baseline versus last observation on treatment - Cohort 12 weeks treatment (Safety Analysis Set)

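### Pulse and blood pressure are named risks, but safety vital signs get no by-arm worst-value, shift or count table, and out-of-range readings are flagged only in listings

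*SAP*

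**What the plan says.** Protocol 1.3 lists, among risks identified in preclinical safety studies, "minimal hypertrophy of thyroid follicular cells and potential effects on heart rate and blood pressure", and says the potential risks will be closely monitored.

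SAP 8.8.4 says vital signs "will be summarized for each treatment group, and for change from baseline at each visit based on the Safety Analysis Set". One table carries this out, Table 14.3.8.1 in SAP section 12. SAP 7.1 gives its content: n, mean, SD, median, minimum and maximum, for values and for changes. For abnormal values, "Vital signs will be also presented in listings including flags for values outside of the reference ranges". The ranges are 80-180 mmHg systolic, 50-120 mmHg diastolic and 50-95 beats/min for pulse.

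SAP 6.2.2 decides which readings reach the table. Readings outside a visit window are labelled unscheduled. If a window holds readings from several days, the day nearest the scheduled day is used. Then: "If several measurements are collected during the selected day, the average (for numeric values)/worst (for categorical values) of the measurements will be taken". Protocol 5.2.5 expects extra readings: vital signs are taken at the scheduled times "and ad-hoc as medically indicated".

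Laboratory values are treated differently. SAP 8.8.3 classes them as low, normal or high and tabulates shifts from baseline to the on-treatment maximum and minimum, by treatment group and cohort.

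**The concern.** A haemodynamic effect confined to a minority of post-ACS patients moves an arm mean only a little. The natural way to see it is to ask how many patients in each arm went out of range at any time on treatment. The plan asks that question for laboratory values but not for pulse or blood pressure, which carry a named risk. The readings most likely to be extreme, those taken because someone was worried, are also the ones most likely to fall outside a window or on a day that is not selected. A reader of the study report would have to count patients from a listing to compare arms.

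**Working it through.** The plan states no figure on this point, so the check sets the rules side by side.

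**Routes by which an abnormal reading could reach a by-arm output**
- By-visit table (SAP 8.8.4): selected readings only. Its minimum and maximum show one extreme per arm and visit, not a number of patients.
- Pulse-wave analysis (SAP 8.7.1): a repeated-measures comparison of each dose with placebo for brachial and central pressure. It is exploratory, uses the Efficacy Analysis Set, tests Visits 4 and 4c, compares means, and does not include pulse.
- ECG: heart rate is recorded (Protocol 5.2.4.1), but SAP 5.2 restricts the summary to the overall evaluation.
- Adverse events: Protocol 6.3.6 makes a deterioration in vital signs an AE only if it meets a seriousness criterion or leads to stopping the product. Accompanying signs or symptoms are reported in their own right.
- Interim safety review: Protocol 8.5.6 names AEs, SAEs and safety laboratory data, and SAP 8.10.3 lists no vital-signs output.

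**Days outside every window** (SAP Table 3; on-treatment phase to last dose + 7, SAP 6.2.3)
- 12-week patient, last dose on Day 84. On-treatment days after Day 1: 2 to 91, so 90 days. Windows: 10-18 (9), 23-33 (11), 49-63 (15) and 74-87 (14, capped at last dose + 3), total 49. Outside: 90 - 49 = 41.
- 4-week patient, last dose on Day 28. Days 2 to 35, so 34 days. Windows: 10-18 (9) and 23-31 (9), total 18. Outside: 34 - 18 = 16.

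These are days, not readings. The documents do not say how many ad hoc readings to expect.

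**Same-day averaging.** Illustrative readings of 78 and 96 mmHg give (78 + 96)/2 = 87 mmHg, inside the range, although one reading was below 80.

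**What the mean shows** (assumed inputs). At 2:1:2, 138 x 2/5 is about 55 patients in each of the larger arms. If 5-10% of one arm fell by 25-35 mmHg, its mean would shift by 0.05 x 25 = 1.25 to 0.10 x 35 = 3.5 mmHg. With an assumed SD of 12-18 mmHg, the standard error of the arm difference is SD x sqrt(2/55) = 2.3 to 3.4 mmHg. The shift is therefore about 0.4 to 1.5 standard errors.

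**Day 1.** SAP 6.2.2 makes every Day 1 vital sign a baseline value. SAP 6.6.4 makes a reading after the first dose on Day 1 an on-treatment value. Both cannot hold for a post-dose Day 1 reading.

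**Limits.** Exclusion criterion 19 is "Systolic blood pressure < 90 mmHg"; the systolic flag starts below 80, a gap of 10 mmHg. Criterion 18 excludes heart rate below 40 bpm; the pulse flag starts below 50, a gap of 10 the other way. A fall to 80-89 mmHg is unflagged, while an eligible patient at 40-49 bpm is flagged from baseline.

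**The case against.** The strongest reply is that the gap is narrow. A large fall at a scheduled visit shows in the minimum-change cell of the by-visit table. An ad hoc reading taken because of symptoms brings an AE for the symptom, which is tabulated by arm. What escapes is mainly an extreme reading without reportable symptoms that falls off the selected day or is averaged away, and the missing patient count. Protocol 8.5.3 promises only a summary by treatment group, which the SAP delivers. Protocol 1.3 reports that none of the preclinical findings were observed in clinical studies so far. All of this stands and keeps the point modest. The earlier experience, however, is in 84 healthy subjects with repeated dosing for up to 10 days, not post-ACS patients over 12 weeks.

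Three stronger readings are tempting and not supported:
- *Blood pressure has no other by-arm analysis.* It has one, the pulse-wave comparison. The statement is right only for pulse and for outlier counts.
- *80 against 90 mmHg is a contradiction.* One is an entry criterion and the other a listing flag. They can serve different purposes, and values of 80-89 are still listed. The difference needs an explanation, not a correction that this review could name.
- *Counting patients is shown to be more powerful than comparing means.* The documents give neither an SD nor event rates. At the present flag limit the systolic count could be small. After a 30 mmHg fall, only patients starting below 110 cross 80. With an assumed baseline mean of 120-130 and SD of 15-18, truncated at 90, a fall in 10% of an arm puts about 1-2.5% of it below 80: 0.55 to 1.4 of 55 patients.

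It is also fair that a bare count outside limits would include patients who entered outside them. A shift from baseline answers that.

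**Conclusion.** The point holds as a modest reporting gap on a named risk. For safety vital signs the plan has no by-arm worst on-treatment value, shift or count, and its windowing rule can drop or average away individual extreme readings. Up to 41 of 90 on-treatment days after Day 1 (12-week cohort) and 16 of 34 (4-week cohort) lie outside every window, assuming last doses on Days 84 and 28. This reads the by-visit table as showing scheduled visits only; the SAP does not say that unscheduled readings get a row. The conflict over Day 1 readings is a plain inconsistency. Nothing here shows that an effect exists or would be missed with a stated probability, and no efficacy conclusion is touched.

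**What to change.** Add to SAP 8.8.4 one table by arm and cohort: shifts from baseline to the lowest and to the highest on-treatment pulse, systolic and diastolic value, classed low, normal or high against the SAP ranges, with number and percentage of patients. Use all individual readings after the first dose to last dose + 7 days, including unscheduled ones, without averaging. State whether readings taken with the CFVR examination stay out, as SAP 8.8.4 now keeps them from statistical analysis.

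Reconcile SAP 6.2.2 and 6.6.4 on readings after the first dose on Day 1. Ask the sponsor to reconcile or explain the flag limits against the entry limits (systolic 80 v 90 mmHg, pulse 50 v 40 bpm); this review does not say which is right.

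The cost is one more descriptive safety table. It uses data already collected and the maximum/minimum method already specified for laboratory values.
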